5.4.2 Secondary Efficacy Analyses

5.4.2.1 Change in actual management plan

The number, percentage and exact 95% CI for the percentage of subjects in the EAS with clinically significant deviations in actual management from the revised management plan after ¹⁸F-fluciclovine PET/CT scan results become available will be presented for overall and for subjects with positive and with negative ¹⁸F-fluciclovine PET/CT scans.

All management plan deviations will be listed in full.

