9.2 Clinical Assessments

Data from the following assessments and procedures should be documented in the Subject's medical records and recorded in the eCRF

1. Concomitant Medications

All concomitant medication and concurrent therapies will be documented at Screening and at all Visits and at End of Follow up. Dose, route, unit frequency of administration, and indication for administration and dates of medication will be captured.

2. Demographics

Demographic information will include age, gender, race and ethnicity.

3. Medical History

Include history of prostate cancer and prostate cancer treatments, and other clinically significant diagnoses. Prostate cancer history should include the date of initial diagnosis, initial tumor stage and Gleason score, dates of definitive therapy and adjuvant treatment (if given), and date of diagnosis of biochemical recurrence.

4. Imaging Studies

Imaging data will include all imaging results (including relevant bone scans, CT etc) from 60 days before screening so the final follow-up and all prostate cancer imaging results available from the Subject's file

5. Vital Signs

Blood pressure and pulse rate will be performed after resting for 5 minutes.

6. 12 lead Electrocardiogram (EKG)

EKG will be recorded as indicated in Section 10. Original EKGs are to be anonymized and forwarded to Clinical Research, Blue Earth Diagnostics, [name] and copies maintained in the Subject's medical record.

7. PSA Levels

PSA levels will be recorded from the Subjects medical records

8. Management Plan

The Intended Management Plan. The treating physician will complete the Management Plan Questionnaire to document his/her intended treatment including planned radiation fields, intended resection limits of surgery, use of brachytherapy, cryotherapy or HiFU, intended use of adjuvant therapy.

The Revised Management Plan. Where an additional diagnostic procedure (e.g., imaging or biopsy) is performed in light of the PET/CT findings, the results of these should be considered prior to recording the revised management plan. Any such diagnostic procedures do not qualify as a "change" to clinical management. The treating physician will complete the Management Plan Questionnaire to document changes to the Pre-scan Management Plan. Changes include such responses as change to radiation or surgical fields. The patient may enter another clinical trial as part of the Revised Management Plan.

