10.6 End of Study (26+/-4 weeks post scan)

The treating physician will complete the Management Plan Questionnaire to document the actual treatment given, including any changes to radiation, surgery, or medications given.

The following data from Visit 2 through to 6 months after the ¹⁸F-fluciclovine PET/CT will be abstracted from the Subject's medical record:

1. All PSA results.
2. All biopsy results and reports.
3. Restaging procedure results (e.g. bone scan or CT/MRI scans).
4. Current prostate cancer status and date of recurrence if applicable.
5. Adverse events reported by the patient
6. Date and cause of death if applicable.

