10.8 Discontinuation/Withdrawal of Subjects

Each Subject has the right to withdraw from the study at any time without giving a reason and without prejudice. In addition, a Subject may be discontinued from the study at any time for any of the following reasons:

- Ineligibility (recognized/arising after registration and prior to ¹⁸F-fluciclovine administration)
- Significant protocol deviation
- Significant non-compliance with study requirements
- Withdrawal of consent
- Loss to follow up
- Investigator discretion

Withdrawal from the study will not result in exclusion of the data for that Subject from analysis provided all baseline study measures have been completed.

The reason for withdrawal, if known, will be recorded in the eCRF.

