14.2 Analysis of Secondary Endpoints

For the evaluation of the secondary endpoint examining actual impact on therapy, questionnaires obtained pre-FACBC will be compared to treatment executed post-¹⁸F-fluciclovine PET/CT to calculate the fraction of cases with a change in management (versus no change in planned management). For the estimation of detection rate, the proportion of the ¹⁸F-fluciclovine -PET/CT positive results, 95% confidence interval will be calculated using the Exact method for a binomial distribution.

For each patient a comparison will be made of the results of the ¹⁸F-fluciclovine PET/CT results, any histopathology results, results of any other imaging and also for the clinical response to treatment(s) (standard of truth) by an Adjudication Panel. The PPV, NPV, sensitivity and specificity will be calculated, where possible, at lesion or regional or patient level. The PPV will be calculated separately for patients undergoing optional biopsy for (1) regional disease and (2) distant disease. The 95% confidence interval will be calculated using the Exact method for a binomial distribution. The Adjudication Panel will follow the Adjudication Manual that will prospectively document the processes to be used to determine a decision concerning the result of the ¹⁸F-fluciclovine PET/CT scan vs standard of truth.

Rates of disease detection (radiographic only and confirmed by pathology or MRI) will be described

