4 STUDY SUBJECTS

4.1 Analysis sets

The list of subjects to be included in each of the analysis sets is to be agreed between the Syne qua non statistician and Blue Earth Diagnostics once all study data are available and prior to database lock.

Enrolled Set: All subjects who entered screening.

Safety Analysis Set (SAF): All subjects who have been included in the database and have been administered ^{18}F -fluciclovine will be included in the Safety Analysis Set (SAF).

Full Analysis Set (FAS): All subjects enrolled who have had an ^{18}F -fluciclovine PET/CT scan will be included in the Full Analysis Set (FAS).

Evaluable Analysis Set (EAS): All subjects from the FAS who have an intended treatment management plan completed and a revised management plan page completed will be included in the Evaluable Analysis Set (EAS).

Per Protocol Set (PPS): All subjects in the EAS who meet the second and third protocol inclusion criteria (see protocol section 6.2) and any other subject without major significant deviation following review of the protocol deviation list.

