5.4.2.4 Treatment response as assessed by change in PSA

Baseline PSA is the most recent PSA measurement prior to salvage therapy for subjects who had salvage treatment and the most recent PSA measurement prior to the ^{18}F -fluciclovine PET/CT for non-salvage subjects. Treatment response, which is based on the percentage change in PSA from baseline to the last value reported, is defined as:

- $\geq 30\%$ decrease in PSA will be considered to be a response to treatment
- $<25\%$ increase or $<30\%$ decrease will be classified as stable disease
- $\geq 25\%$ increase in PSA will be classified as disease progression

The number, percentage and exact 95% CI of subjects having a treatment response, stable disease and disease progression, as assessed by change in PSA, will be presented overall and separately for subjects in the EAS who had salvage treatment, for subjects who had non-salvage treatment, for those with a change in management plan and for subjects with no change in management plan, by treatment and by disease location (Local disease/Extra-prostatic disease) following the ^{18}F -fluciclovine PET/CT scan.

In addition, the percentage change in PSA from baseline to the last value reported will be summarised overall and by subjects who had a change in management plan versus those who did not have a change in management plan following the ^{18}F -

fluciclovine PET/CT scan. The percentage change in PSA from baseline to the last value reported will also be summarised for subjects who had disease in the prostate only and for subjects who have extra-prostatic disease and by treatment.

Finally, a waterfall plot of the maximum percentage reduction in PSA during the 4-8 month window will be presented on the y-axis and each subject will be represented by a bar on the x-axis. The bars will be ordered in descending order of the magnitude of the percentage change in PSA value.

Treatment response and the factors used to assess the response will be listed in full.

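### SAP 5.4.2.1 compares actual treatment with the revised plan instead of the intended plan; once that is corrected, the evaluable-set restriction there and on PSA response drops usable men needlessly

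*SAP*

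**What the plan says.** **The declared endpoint.** Protocol 3.2 (objective 1), Protocol 5.2 (endpoint 1) and SAP 5.2 all set the pre-scan intended plan against actual management. Protocol 14.2 describes the analysis in the same terms: "questionnaires obtained pre-FACBC will be compared to treatment executed post" the scan. The source for the second half is the End of Study visit in Protocol 10.6: "The treating physician will complete the Management Plan Questionnaire to document the actual treatment given".

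**The planned analysis.** SAP 5.4.2.1 gives "The number, percentage and exact 95% CI for the percentage of subjects in the EAS with clinically significant deviations in actual management". The sentence goes on to name the revised plan, not the intended plan, as the reference. SAP 3.5, which lists changes from the protocol's analysis, mentions only the positive predictive value.

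**The analysis set.** SAP 4.1 defines the EAS as "All subjects from the FAS who have an intended treatment management plan completed and a revised management plan page completed". The Full Analysis Set (FAS) is everyone enrolled who was scanned.

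**PSA response.** SAP 5.4.2.4 computes response from the percentage change between baseline and last PSA. The response categories "will be presented overall and separately for subjects in the EAS who had salvage treatment", and then by non-salvage treatment, by change or no change of plan, by treatment and by disease location. The paragraphs on percentage change and on the waterfall plot name no analysis set.

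**The concern.** No analysis in SAP 5.4 compares intended with actual management. SAP 5.4.1 compares intended with revised, and SAP 5.4.2.1 compares revised with actual. The endpoint that shows what was done, as opposed to what was planned, therefore has no table.

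Restoring the comparator would not be enough. If the analysis stays in the EAS, a scanned man with an intended plan and a record of treatment given is still left out because a third form, which the comparison does not use, is absent. The same happens to a man with usable PSA values in the response categories. Neither section has an FAS version, and SAP 2 and 5.4.3 rule out imputation, so these men enter no planned estimate of management change. The primary and secondary results could then agree partly because both omit the same men.

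**Working it through.** **Step 1. Which records each analysis needs.**

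| Analysis | Intended plan | Revised page | Treatment given | PSA values |
|---|---|---|---|---|
| Declared endpoint (Protocol 14.2, SAP 5.2) | yes | no | yes | no |
| SAP 5.4.2.1 as written | no | yes | yes | no |
| PSA categories: overall, salvage/non-salvage, by treatment, by location (location also needs the scan result) | no | no | yes | yes |
| PSA categories: by change of plan | yes | yes | yes | yes |

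The EAS requires the first two columns. It fits the second and fourth rows. For the first and third rows it asks for a page that is not used.

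**Step 2. The two comparators answer different questions.** Take a man whose plan changed after the scan and who was treated to the revised plan. The declared endpoint counts a change; SAP 5.4.2.1 counts no deviation. Now take a man whose plan was revised but who received the treatment first intended. The declared endpoint counts no change; SAP 5.4.2.1 counts a deviation, if it is judged clinically significant. One result cannot stand in for the other.

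**Step 3. The plan's own figures.** No sample size is given for these secondary analyses. The chain for the primary aim (Protocol 14.4) reproduces:
- Clopper-Pearson 95% limits at 30% with n = 89 are 0.207 to 0.406, width 0.199, as stated.
- 89 / 0.40 = 222.5, so 223, as stated.
- 248 enrolled gives a 0.918 probability of at least 89 positive scans, which meets the stated 90%.
- 248 / (1 − 0.15) = 291.8, so 292, as stated.

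**Step 4. How far the exclusion could move the estimate.** The documents give neither the share of men lacking only the revised page (m) nor a rate of actual change, so what follows is illustration. I take 30% as the rate in the EAS. It is borrowed from Protocol 14.4, where it refers to positive scans and to intended change. I take 292 as the number scanned. With r the rate among excluded men:

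rate in all scanned = (1 − m) × 0.30 + m × r, so the shift from the EAS figure is m × (r − 0.30).

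| m | men excluded | r = 10% | r = 30% | r = 50% |
|---|---|---|---|---|
| 5% | 15 | 29.0% | 30.0% | 31.0% |
| 10% | 29 | 28.0% | 30.0% | 32.0% |
| 15% | 44 | 27.0% | 30.0% | 33.0% |

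The 15% row treats all the planned data loss as missing revised pages, so it is an upper bound. At that bound the extremes r = 0% and r = 100% give 0.85 × 0.30 = 25.5% and 0.255 + 0.15 = 40.5%.

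**Step 5. Precision.** At 30%, the exact 95% interval is 0.118 wide with 248 men and 0.108 wide with 292. The loss is about 0.01.

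**The case against.** The strongest reply is that SAP 5.4.2.1 as written cannot be computed without the revised page, so the EAS is the right set for it. That is correct. A reader might infer that the revised page is irrelevant to the analysis as it stands, and the text does not support that. The root fault is the comparator; the EAS becomes an avoidable restriction only after it is corrected. Protocol 9.2 also describes actual management as departures from the revised plan, which gives the SAP some cover, and Protocol 14 lets the SAP modify the analyses. But SAP 5.2 still declares intended versus actual, and SAP 3.5 announces no change, so the SAP disagrees with itself.

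A reader might also infer that men under PET-prompted work-up are the ones who lose the form, because in Protocol 9.2 "the results of these should be considered prior to recording the revised management plan". That passage shows delay, not absence. The EAS sets no time limit, so a page completed after day 22 still qualifies. A link with outcome is possible, but nothing in the documents demonstrates one.

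Protocol 10.8 might be read as forbidding the exclusion: "Withdrawal from the study will not result in exclusion of the data for that Subject from analysis provided all baseline study measures have been completed". It concerns withdrawal, and a man with an End of Study record need not have withdrawn. It supports the principle of keeping data but does not contradict the EAS.

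On size, the 15% covers every kind of data loss. It includes men lost before 6 months, whom this change would not recover, so the share lacking only the revised page may be well below it. A 1-point shift is small beside an interval half-width of nearly 6 points (0.118 / 2 = 0.059).

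PSA response is not among the secondary variables in SAP 5.2, and the EAS is named only for the response categories, so it would be wrong to say that all PSA summaries are confined to it.

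Finally, SAP 4.2 lists EAS membership with reasons for exclusion, and SAP 5 bases efficacy listings on the FAS. Excluded men therefore remain visible, and a denominator shared with the primary table is defensible. That stands, but a listing is not an estimate.

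**Conclusion.** The point holds in two linked parts. First, SAP 5.4.2.1 replaces the declared intended-versus-actual comparison with revised-versus-actual and does not record the change. This follows from the text alone. Second, once the comparator is restored, requiring a revised page needlessly drops scanned men who hold both records, and the same is true of the PSA response categories other than the splits by change of plan.

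Whether that exclusion biases anything is unknown. Under the assumptions in the working, the shift is about ±1 point at 5% missing and ±3 points at 15%, and zero if excluded men do not differ. The precision cost is minor. The primary endpoint is not affected. The change is worth making because it restores the endpoint the plan declares and removes an avoidable selection, not because a large bias has been shown.

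**What to change.** - **SAP 5.4.2.1:** compare intended with actual management in all FAS subjects who have an intended plan and an End of Study actual-management record, overall and by PET result. Keep the revised-versus-actual table in the EAS as supporting.
- **SAP 5.4.2.4:** use FAS subjects with a baseline and a post-baseline PSA for the overall, salvage/non-salvage, by-treatment and by-location summaries. Name that set for the percentage-change and waterfall summaries too. Keep the EAS only for splits by change of management plan.
- **Check:** confirm that the End of Study form records the treatment given in its own right, as Protocol 10.6 says, and not only departures from the revised plan, as Protocol 9.2 could be read.

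The cost is a few sentences of SAP text and one extra table. If that check is satisfied, no new data are needed. The downside is that denominators will differ slightly from the primary table, which a footnote can explain.

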3.2 Secondary Objectives

1. To measure the fraction of patients for whom ^{18}F -fluciclovine PET/CT leads to a change of actual management by comparison with the intended management plan before ^{18}F -fluciclovine PET/CT.
2. To estimate the fraction of patients in whom ^{18}F -fluciclovine PET/CT yields evidence of recurrent disease on the basis of imaging results.
3. To estimate 1) the rates of detecting regionally recurrent disease (i.e., prostatic bed-only and/or pelvic disease outside of the bed) and 2) the rate of detecting distant metastases (i.e., bone metastases, visceral metastases, or non-regional nodal metastases) with ^{18}F -fluciclovine PET/CT in the study population.
4. To determine 1) the PPV of ^{18}F -fluciclovine PET/CT to detect regionally recurrent disease and 2) the PPV of ^{18}F -fluciclovine PET/CT to detect distant metastases in the study population in patients who undergo optional biopsy of ^{18}F -fluciclovine PET/CT findings or have documentation of disease status based on other imaging and/or follow-up data. For soft tissue disease these calculations will be limited to those patients who undergo a confirmatory biopsy and for bone disease those with confirmatory findings on MRI any time during the 6-month follow up. The denominator for the analysis will be [lesions biopsied + bone lesions].
5. To explore differences in estimated cost of treatment plans determined prior to and following ^{18}F -fluciclovine PET/CT.

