5.2 Secondary Efficacy Endpoints

1. Per-patient impact (yes/no) of ^{18}F -fluciclovine PET/CT on pre-PET intended versus post-PET actual patient management (assessed at 6 months post scan)

2. The rate of detection of any disease site by ^{18}F -fluciclovine PET/CT in the study population;
3. The rate of detection of 1) prostatic bed and other pelvic disease and 2) distant metastases (i.e., bone metastases, visceral metastases, or non-regional nodal metastases) with ^{18}F -fluciclovine PET/CT in the study population;
4. The PPV of ^{18}F -fluciclovine PET/CT to detect regionally recurrent disease compared to biopsy in those patients who undergo a regional disease biopsy on the basis of a ^{18}F -fluciclovine PET/CT finding or in case of bony disease a correlation with MRI or biopsy.
5. The PPV of ^{18}F -fluciclovine PET/CT to detect distant disease compared to biopsy in those patients who undergo a distant disease biopsy on the basis of a ^{18}F -fluciclovine PET/CT finding or in case of bony disease a correlation with MRI or biopsy.

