Actual Management Plan. At the final follow up visit any deviations or changes to the Revised Management Plan will be documented

9. Biopsy

Biopsy is not required by the protocol; however patients with PET/CT positive findings in soft-tissue supported by anatomical abnormalities on CT or MRI may have a biopsy performed per standard practice where the procedure is deemed clinically feasible and safe. Biopsies completed within 4 months after imaging will contribute to the aim of the study.

1. Biopsy results of suspected bone metastases conducted per standard practice will also be collected. Bone lesions may be followed up through imaging where biopsy is not practical.
2. Based on local-radiologist/nuclear medicine physicians assessment of ¹⁸F-fluciclovine PET/CT-positive findings supported by anatomic abnormalities, conduct imaging-guided biopsy of soft-tissue ¹⁸F-fluciclovine -enhancement region per institutional standard of care;
3. Submit pathology report(s) to the ACR Core Laboratory. The address is given in the Imaging Manual.

10. Blood Chemistry Profile

Blood will be obtained and sent to each site's clinical chemistry lab for determination of serum sodium, potassium, calcium, chloride, BUN, creatinine, glutamic oxaloacetic transaminase (SGOT/AST), glutamic-pyruvic transaminase (SGPT/ALT), alkaline phosphatase, creatine kinase (CK), lactate dehydrogenase (LDH), albumin, total protein, total bilirubin.

11. Hematology

Blood will be obtained and sent to each site's clinical hematology lab for a complete blood count (hemoglobin, hematocrit, red blood cell count, white blood cell count, white blood cell differential, and platelet count determinations).

12. Urinalysis

Prior to the ¹⁸F-fluciclovine dosing a midstream sample of urine will be obtained and tested by dipstick for leukocytes, nitrite, pH, protein, ketones, glucose, bilirubin, urobilinogen, and blood. This will not be repeated following scanning unless clinically indicated.

13. Adverse Events

See Section 12.

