3 STUDY OBJECTIVES AND DESIGN

3.1 Study Objectives

The primary objective of the study is to measure the fraction of subjects for whom ¹⁸F-fluciclovine PET/CT alters intended management through detection of disease after curative-intent treatment in a population of men with elevated prostatic specific antigen (PSA) levels indicative of persistent or recurrent prostate cancer and negative or equivocal findings on standard-of-care diagnostic imaging tests.

The secondary objectives of the study are

- To measure the fraction of subjects for whom ¹⁸F-fluciclovine PET/CT leads to a change in actual management by comparison with the intended management plan before ¹⁸F-fluciclovine PET/CT
- To estimate the fraction of subjects in whom ¹⁸F-fluciclovine PET/CT yields evidence of recurrent disease on the basis of imaging results
- To estimate:

- the rates of detecting regionally recurrent disease (i.e. prostatic bed-only and/or pelvic disease outside of the bed)
 - the rate of detecting distant metastases (i.e. bone metastases, visceral metastases, or non-regional nodal metastases)
- with ^{18}F -fluciclovine PET/CT in the study population
- To determine:
 - the positive predictive value (PPV) of ^{18}F -fluciclovine PET/CT to detect regionally recurrent disease
 - the PPV of ^{18}F -fluciclovine PET/CT to detect distant metastases in the study population in subjects who undergo optional biopsy of ^{18}F -fluciclovine PET/CT findings or have documentation of disease status based on other imaging and/or follow-up data
 - To explore differences in estimated cost of treatment plans determined prior to and following ^{18}F -fluciclovine PET/CT

[figure not shown]

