3.5 Changes from the Protocol Planned Analysis

PPV efficacy variable (section 5.2) will be determined using adjudication panel decision rather than only using biopsy or biopsy/MRI data. This is consistent with the study objectives.

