5.2 Secondary Efficacy Variables

The secondary efficacy variables are:

- Per subject impact (yes/no) of ^{18}F -fluciclovine PET/CT on pre-PET intended versus post-PET actual subject management
- The rate of detection of any disease site by ^{18}F -fluciclovine PET/CT in the study population
- The rate of detection of:
 - Prostatic bed and other pelvic disease
 - Distant metastases (i.e. bone metastases, visceral metastases or non-regional nodal metastases)with ^{18}F -fluciclovine PET/CT in the study population
- The PPV of ^{18}F -fluciclovine PET/CT to detect regionally recurrent disease compared to adjudication panel decision.
- The PPV of ^{18}F -fluciclovine PET/CT to detect distant metastases compared to adjudication panel decision.

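### SAP 5.4.2.1 compares actual management with the revised post-scan plan, but the first secondary endpoint compares it with the intended pre-scan plan

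*SAP*

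**What the plan says.** The endpoint is stated consistently, with the pre-scan intended plan as comparator:

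- Protocol 3.2, objective 1: the scan "leads to a change of actual management by comparison with the intended management plan before" the scan. The synopsis says the same.
- Protocol 5.2, endpoint 1: a per-patient yes/no comparison of pre-scan intention with actual management, assessed at 6 months.
- Protocol 14.2: "questionnaires obtained pre-FACBC will be compared to treatment executed" after the scan.
- SAP 3.1: the scan "leads to a change in actual management by comparison with the intended management plan before" the scan.
- SAP 5.2: per-subject impact "on pre-PET intended versus post-PET actual subject management".

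The analysis text is different. SAP 5.4.2.1 gives the number, percentage and exact 95% CI of "subjects in the EAS with clinically significant deviations in actual management from the revised management plan", overall and by scan result.

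Protocol 14 says the SAP will contain any modification of the planned analysis. SAP 3.5 lists one: "PPV efficacy variable (section 5.2) will be determined using adjudication panel decision rather than only using biopsy or biopsy/MRI data". It does not mention the comparator for actual management.

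**The concern.** The SAP contradicts the protocol and its own sections 3.1 and 5.2. The statistic in 5.4.2.1 answers another question: did physicians do what they wrote down after the scan? The endpoint asks whether delivered care differed from what was intended without the scan. It is the plan's only estimate of change in care given rather than care planned.

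The section also keeps only deviations judged clinically significant, a filter that it does not define and that the endpoint does not contain.

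Two further points are left open:

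- **Source of actual treatment.** Protocol 9.2 (item 8) says "At the final follow up visit any deviations or changes to the Revised Management Plan will be documented", whereas Protocol 10.6 has the physician record the treatment actually given.
- **Denominator.** Membership of the Evaluable Analysis Set (SAP 4.1) needs an intended and a revised plan but no record of actual management. SAP 2 makes the whole analysis set the default denominator. Subjects with no record of actual management would therefore stay in the denominator and could not count as changed.

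**Working it through.** **1. Subject by subject.** The possible patterns, with each deviation taken as clinically significant:

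| Revised plan vs intended | Treatment given | Endpoint: actual differs from intended | SAP 5.4.2.1: actual differs from revised |
|---|---|---|---|
| Same | As planned | No | No |
| Same | Something else | Yes | Yes |
| Changed | As revised | Yes | **No** |
| Changed | Back to intended | No | **Yes** |
| Changed | A third option | Yes | Yes |

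The two measures disagree in rows 3 and 4, so endpoint minus SAP figure = (fraction changed and treated as revised) minus (fraction changed and returned to the intended plan).

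**2. Inputs.** The documents give no expected value for this endpoint. They assume 40% positive scans and a 30% plan-change rate among positives (Protocol 14.4, SAP 3.4). Their precision figure reproduces: the Clopper-Pearson interval at 30% with n = 89 is 0.207 to 0.406, width 0.199. Let c be the fraction of plans changed and d the fraction deviating from the revised plan. The SAP reports d, or less once the clinical-significance filter is applied. The documents give no adherence rate, so every value of d is an assumption. I use c = 0.30 (the rate in positives) and c = 0.40 × 0.30 = 0.12 (all subjects, if no negative scan changes a plan).

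**3. Full adherence, d = 0.** The SAP figure is 0 and the endpoint equals c. With 89 positives, 0.30 × 89 = 26.7, rounded to 27:

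- SAP: 0/89 = 0% (exact 95% CI 0 to 4.1%)
- Endpoint: 27/89 = 30.3% (21.0 to 41.0%)

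**4. Partial adherence.** If changed and unchanged subjects deviate at the same rate, the endpoint runs from c(1 − d) + (1 − c)d, when every changed deviator returns to the intended plan, to c + (1 − c)d, when none does. Without equal adherence, it can lie anywhere from |c − d| to c + d. For c = 0.12 and d = 0.05, the equal-adherence range is 0.12 × 0.95 + 0.88 × 0.05 = 0.158 to 0.12 + 0.88 × 0.05 = 0.164. In full:

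| c | d = SAP figure | Endpoint, equal adherence | Endpoint, any pattern |
|---|---|---|---|
| 0.12 | 5% | 15.8–16.4% | 7–17% |
| 0.12 | 20% | 27.2–29.6% | 8–32% |
| 0.30 | 5% | 32.0–33.5% | 25–35% |
| 0.30 | 20% | 38–44% | 10–50% |

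One SAP figure is thus compatible with very different endpoint values.

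**5. Scale in the whole study.** 292 × 0.85 gives 248 evaluable subjects. For c = 0.12 and d = 0.05, rounded counts are 12/248 = 4.8% (exact 95% CI 2.5 to 8.3%) for the SAP and 40/248 = 16.1% (11.8 to 21.3%) for the endpoint. These intervals do not overlap.

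**The case against.** The strongest reply is that the information is not lost. SAP 5.4.1 lists intended and revised plans, 5.4.2.1 lists all plan deviations, and 4.4.4 tabulates and lists prostate cancer therapies, including those started after injection. Intended versus actual could probably be derived from these. That is fair, but a listing is not the pre-specified proportion with its interval. SAP 5.4.1 covers only intended versus revised, and the table shells are a separate document that cannot be assumed to correct the text.

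Other points carry some weight:

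- SAP 4.4.4 and 5.4.2.4 also use treatments received, but neither compares them with the intended plan.
- Protocol 9.2 and 10.6 need not conflict. The questionnaire is not in the documents, so what it captures is unknown. A data-collection instruction does not redefine the endpoint in any case.
- The denominator rule is a separate matter that would arise with the right comparator too.
- The adherence rates are assumed. The 12% case also supposes that negative scans never change plans, although the protocol's rationale expects that a negative scan could delay systemic therapy. The intervals show scale and are not forecasts.
- This is a descriptive secondary estimate with no hypothesis test, so its priority can be argued.

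None of this removes the undeclared mismatch of comparator.

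**Conclusion.** The concern holds, with high confidence. Followed as written, the SAP leaves its first secondary endpoint without a specified summary estimate and reports adherence to the post-scan plan in its place. The secure result needs no adherence figure: the SAP statistic is 0% under full adherence whatever the scan changed. The size in practice depends on unknown adherence. Under the illustrative assumptions, a SAP figure of 5% goes with an endpoint of about 16% or 33% when adherence is equal, and anywhere from 7% to 35% across the two change rates when it is not. The effect is confined to this secondary estimate. It should be corrected before database lock because it is an undeclared departure from the endpoint and is cheap to put right.

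**What to change.** Rewrite SAP 5.4.2.1 along these lines: *The number, percentage and exact 95% CI of subjects whose actual management differs from the intended pre-scan plan will be presented, overall and by scan result.* The yes/no result is what the endpoint requires. The no/major/other split of SAP 5.4.1 can be added by extending its grouping table, which now covers only original and revised plans, to actual treatment.

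Then:

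- State the source of actual treatment: the end-of-study questionnaire, or the revised plan plus recorded deviations if the form captures only those.
- State the denominator, for example Evaluable Analysis Set subjects with a record of actual management, and report the number and percentage without one. This comparison does not itself need a revised plan, so say whether subjects lacking only that are included.
- Keep actual versus revised as a separate descriptive adherence table, and define or drop the clinical-significance filter.
- If the sponsor does want the revised-plan comparator, declare it in SAP 3.5 and align 3.1 and 5.2.

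The cost is SAP wording, one more column in the grouping table and limited programming. If the eCRF holds only deviations, reconstructing actual treatment adds derivation work. No new data from subjects are needed.
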